# Table of Contents

	1.OBJECTIVES	
	2.BACKGROUND	6
	2.1.Study Disease	6
	2.2.Study Agent/Device/Imaging procedure	7
	2.3.Clinicaltrials.gov	8
	3. Participant population	
	3.1.Inclusion Criteria	8
	3.2.Exclusion Criteria	9
	4.STUDY PROCEDURE:	0
_	_4.510D1 PROCEDURE	9
	_ 5. ADVERSE EVENTS AND REPORTING PROCEDURE	
	6.REGULATORY CONSIDERATIONS	10
	6.1.Data and Safety Monitoring Plan	10
	6.2.Confidentiality	
	7.MEASUREMENTS	
	7.1.Primary and Secondary Outcome measures	10
	7.2.Measurement Methods	10
	7.3.Measurement Time Points	10
	7.4.Response Review	
	7.5.Secondary Outcome	
	8.STATISTICAL CONSIDERATIONS	
	8.1.Statistical Design	
	8.2.Randomization	
	8.3.Interim analyses	
	8.4.Descriptive Statistics and Exploratory Data Analysis	
	8.5.Primary Analysis	
	8.6.Secondary Analysis	
	8.7.Sample Size	
	8.8.Accrual estimates	
	8.9.Criteria for future studies	_
	9.REFERENCES	12

TITLE	 F-FSPG PET/MRI or PET/CT Imaging of Cardiac Sarcoidosis or Inflammation
STUDY PHASE	2
INDICATION	Suspected cardiac sarcoid
INVESTIGATIONAL PRODUCT OR PROCEDURE	 F-FSPG
PRIMARY OBJECTIVE(S)	To evaluate if  F-FSPG PET/MRI or PET/CT will identify cardiac sarcoid
SAMPLE SIZE	20
GOALS	To allow the referring physicians in the cardiology group to provide their patients a specific molecular imaging test for sarcoidosis.
	To improve the PET/MRI or PET/CT protocol.

# **SCHEMA**

# LIST OF ABBREVIATIONS AND DEFINITION OF TERMS

F-18	Fluorine-18
IRB	Institutional Review Board
IV	Intravenous
PET/MRI	Positron emission tomography – magnetic resonance imaging
SUV	Standardized Uptake Value
FSPG	(4S)-4-(3-18F-Fluoropropyl)-L-Glutamate

### 1. OBJECTIVE

We hypothesize that increased F-FSPG uptake will be detected in cardiac sarcoid or inflammation using PET/MRI or PET/CT.

#### 2. BACKGROUND

[figure not shown]
### 2.1. Study Disease

Sarcoidosis is a multisystem granulomatous disorder of unknown etiology, which can result in myocardial inflammation [1]. Myocardial inflammation can also result from other causes including myocarditis. Identifying cardiac involvement in the setting of sarcoidosis or myocarditis remains challenging. Approximately 5% of patients with sarcoidosis have clinically apparent cardiac involvement, yet autopsy series indicate that cardiac involvement is present in up to 25% of cases [1]. The diagnostic yield of endomyocardial biopsy is reported at less than 20% [2].

Previous studies have demonstrated high diagnostic accuracy of both cardiac magnetic resonance imaging (MRI) [3-5] and 18F-labelled fluoro-2-deoxyglucose (FDG) positron emission tomography (PET) [6, 7] for detection of cardiac sarcoidosis and myocardial inflammation. To date, simultaneous PET/MRI evaluation of cardiac sarcoidosis has only been described in limited case reports [8]. Despite relative success, patient compliance is affected by the need for 12 hours low-carb diet prior to the scan [9]. Therefore, other radiopharmaceuticals should be investigated.

System xC- is composed of xCT and 4F2hc, mediating cellular cystine uptake for glutathione synthesis to protect cells from oxidative stress [10]. System xC- may play a role in the innate and adaptive immune system. Upregulation of system xC- expression was observed in activated macrophages and granulocytes [11]. Induction of system xC-may be an autoprotective mechanism from the high levels of released reactive oxygen species. Activation of T-lymphocytes has been reported to involve expression of system xC- in antigen-presenting cells [12]. Upregulation of xCT occurs during activation and differentiation of B lymphocyte. On the other hand, very low or no expression of xCT was detected in peripheral leukocytes, thymus, spleen, and lymph nodes in humans [13]. These results suggest that system xC-is a key player in the active phase of inflammation.

(4S)-4-(3-18F-Fluoropropyl)-L-Glutamate (18F FSPG) is a L-glutamate derivative that is specifically taken up by system xC- as previously demonstrated in tumor models and cancer patients [14, 15]. 18F FSPG has also demonstrated increased uptake in inflammation and infection [16]. PET imaging with 18F FSPG does not require a diet or special preparation prior to the scan; hence, we expect increased patient compliance when compared to 18F FDG in the evaluation of cardiac sarcoidosis or inflammation.

**Figure 1**. 53 year old man with sarcoidosis: 18F-FDG (A) and 18F-FSPG (B) present similar major uptake involving pleura, supraclavicular lymph nodes, and thoracic lymph nodes. Sun Young Chae et al. J Nucl Med 2016;57:67-69.

# 2.2. Study Agent/Device/Imaging procedure

# F-FSPG PET/MRI or PET/CT Imaging of Cardiac Sarcoidosis or Inflammation

**Methods:** Here we will evaluate the detection of cardiac sarcoidosis or inflammation using F-FSPG PET/MRI or PET/CT. PET/CT will be used for patients with metal implants who are not eligible for MRI due to safety reasons. We will recruit patients from Division of Cardiology (Sarcoidosis Clinic) at Stanford University. We plan to recruit a total of 50 patients over 4 years who have suspected cardiac sarcoidosis or inflammation, after receiving F FDG PET/CT as standard of care. Potential subjects will undergo preliminary evaluation to ensure eligibility, receive and sign an informed consent and be enrolled in the trial.

PET/MRI scans will be performed with a whole-body PET/MR imaging system capable of simultaneous PET and MR imaging (SIGNA, GE Healthcare, Milwaukee, WI), 45-60 minutes after injection of (+/-20%) 8 mCi of F-FSPG. The system consists of a 3T MR imager that contains a PET detector based on lutetium oxyorthosilicate scintillators coupled to silicon photomultiplier detector (SiPM) technology. PET events will be detected throughout the entire cardiac MRI acquisition in one bed position centered over the heart. A coronal T1-weighted 3D encoded spoiled gradient-echo sequence will be acquired for attenuation correction.

Cardiac MRI sequences will include breath-hold, ECG-triggered balanced cine SSFP for assessment of ventricular size and function by a stack of short axis slices (slice thickness 8 mm, TR 3.0 ms, TE 1.5 ms, flip angle 50°, temporal resolution 35 ms; in-plane resolution 1.7×1.4 mm), and two-dimensional (2D) turbo inversion-recovery magnitude T2-weighted imaging in short axis for assessment of myocardial inflammation and edema (slice thickness 8 mm, TR 2000 ms, TE 44 ms, flip angle 180°, inversion time 180 ms, in-plane resolution 1.3×1.4 mm). Late gadolinium enhanced (LGE) imaging will be performed 15 minutes following administration

of 0.15 mmol/kg bodyweight of MultiHance (Bracco Diagnostics Inc, Monroe Township, NJ) employing a 2D inversion recovery gradient-recalled echo sequence (IR GRE) in short-axis (slice thickness 8 mm, TR 6.5 ms, TE 1.5 ms; flip angle 20°; inversion times 220-360 ms; in-plane resolution 1.8×1.4 mm). Two-, three- and four-chamber LGE planes will also be obtained.

PET/CT will be performed using Discovery MI PET/CT scanner (GE Healthcare). In brief, PET/CT images will be acquired in 3D mode approximately 45-60 minutes after injection of F FSPG. First, a vertex to mid-thighs scan is done, followed by dedicated imaging of the heart over 1 bed. ToF is standard on the digital PET/CT system. Data driven gating will be acquired according to the vendor's protocol (once commercially available). The PET emission scan is corrected using segmented attenuation data of the CT scan. The PET images are reconstructed both with a standard iterative algorithm (OSEM, two iterative steps, 28 subsets), as well as a regularized reconstruction algorithm (Q.Clear®) provided by GE Healthcare.

**Interpretation of Results:** All images are reformatted into axial, coronal, and sagittal views and viewed with the software available in the Nuclear Medicine and Molecular Imaging Clinic (MIM Vista). PET images will be interpreted by two radiologists in consensus ([name] and [name]). A third reader ([name]) will serve as referee to achieve consensus.

PET image interpretation will begin with identification of areas of myocardial F-FSPG uptake on PET/MRI images using multi-planar reformations and maximum-intensity projections. Myocardial F-FSPG uptake will be globally classified into one of four patterns (none, diffuse, focal, or focal on diffuse) for each participant. Diffuse, focal and focal on diffuse patterns of F-FSPG uptake will be considered to be positive findings indicative of cardiac involvement. Myocardial segments will be evaluated for focal F-FSPG activity using the 17-segment model recommended by the American Heart Association (AHA). The presence or absence of RV free wall F-FSPG activity will also be evaluated. The whole-body PET/MRI or PET/CT acquisition will be evaluated for findings of extra-cardiac sarcoid.

For cardiac MRI analysis, left and right ventricular (LV and RV) endocardial borders will be manually contoured on short-axis SSFP images to assess for end-diastolic and end-systolic volumes, and ejection fraction (EF). LV epicardial borders will also be manually contoured to assess LV mass. Presence of T2-hyperintensity and LGE will be qualitatively assessed by visual inspection of all available images and will be graded as present or absent using the AHA 17-segment model. The pattern of LGE will be classified as either CAD type or non-CAD type as described previously [17]. The presence or absence of RV free wall LGE was also evaluated.

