#### 5. ADVERSE EVENTS AND REPORTING PROCEDURES.

The administration of the radioactive substance will feel like a slight pinprick when given by IV injection. Patients who are claustrophobic may feel some anxiety while positioned in the scanner. Also, some patients find it uncomfortable to hold one position for more than a few minutes. The subjects will not feel anything related to the radioactivity of the substance in their body. Because the radioactivity is very short-lived, the radiation exposure is low. The substance amount is so small that it does not affect the normal processes of the body.

This research study involves exposure to radiation from one F-FSPG PET/MRI scan. The effective dose from one typical administration of F-FSPG is 4.5 mSv, approximately equal to 10% of the limit that radiation workers (for example, a hospital x-ray technician) are allowed to receive in one year. This radiation exposure is for research purposes only.

In case you cannot undergo MRI due to metal implants, PET/CT will be done. CT in PET/CT will add 5 mSv for a total of 9.5 mSv, approximately equal to 20% of the limit that radiation workers (for example, a hospital x-ray technician) are allowed to receive in one year.

Adverse events will be graded according to CTCAE v5.0. Both Serious and Non-Serious Adverse Events will be clearly noted in source documentation and listed on study specific Case Report Forms (CRFs). The Protocol Director (PD) or designee will assess each Adverse Event (AE) to determine whether it is unexpected according to the Informed Consent, Protocol Document, or Investigator's Brochures, and related to the investigation. All Serious Adverse Events (SAEs) will be tracked until resolution and 30 days after the last dose of the study treatment.

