### 7. MEASUREMENTS

N/A. This is a pilot study evaluating feasibility of the exam as measured by completed exams and diagnostic quality images.

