## 8. STATISTICAL CONSIDERATIONS

N/A. This is a small pilot study with no statistical analysis included.

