### 8.1. Criteria for future studies

If sarcoid is identified in more than 50% of the cases, a larger study will be planned.

Appendix: Inclusion/Exclusion	n Criteria Checklist						
Protocol Title:	rotocol Title:  18F-FSPG PET/MRI or PET/CT Imaging of Cardiac Sarcoidosis or Inflammation						
Protocol Number:	IRB-40376						
Principal Investigator:	[name]						
In the size Oritania - Management II	4 -        -  -  -  -  -  -  -  -	ſ			0		
Inclusion Criteria – Yes must be (From IRB approve		Yes	No		Supporting Documentation		
1. Patient is ≥ 18 years old at the					Documentation		
1. I duent is = 10 years old at a	ic time of the soan						
2. Patient with known or suspe	cted cardiac sarcoidosis						
Patient is capable of comply procedures	ing with study						
Patient can remain still for deprocedure	uration of imaging						
		r	•	Г			
Exclusion Criteria – No must be (From IRB approve		Yes	No	N/A	Supporting Documentation		
1. Patient is pregnant or nursing	g						

Metallic implants (contraindic patients will get PET/CT)

	ated for MRI; these						
History of renal insufficiency administration)	(only for MRI contrast						
*All subject files must include sup confirmation can include, but is no self-report, and medical record re  i. Stateme  By signing this form of this trial, study. This study is approved by IRB, and has finalized financial	ot limited to, laboratory to eview. I verify that this subject to the Stanford Cancer In	est resul is [□elio stitute S	ts, rad gible / scientif	iology □ inel ic Rev	test results, subject ligible] for participation ir iew Committee, the Star		
Research Management Group.	·	2-4					
PI/ SubPI Signature:	Date:						
Printed Name:							
Secondary Reviewer Signature:							
Printed Name:							
Study Coordinator Signature:		Date:					

Printed Name:

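### The protocol gives two planned sample sizes, 20 in the synopsis and 50 in section 2.2, and nothing links them

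*Protocol*

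**What the plan says.** The synopsis table in the protocol's front matter reads "SAMPLE SIZE 20". Section 2.2, under Methods, reads "We plan to recruit a total of 50 patients over 4 years who have suspected cardiac sarcoidosis or inflammation", and goes on to say that potential subjects are checked for eligibility, give consent and are enrolled. Both the synopsis and section 2.2 cover PET/MRI and PET/CT.

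The table of contents lists subsections on sample size (8.7) and accrual (8.8). In the body, section 8 is marked not applicable: "This is a small pilot study with no statistical analysis included". Section 7 describes the aim without giving a number: "This is a pilot study evaluating feasibility of the exam as measured by completed exams and diagnostic quality images". The one rule that uses the trial's result is in section 8.1: "If sarcoid is identified in more than 50% of the cases, a larger study will be planned".

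Section 5 puts the effective dose of one tracer administration at 4.5 mSv and states: "This radiation exposure is for research purposes only". For patients who cannot have MRI, "CT in PET/CT will add 5 mSv for a total of 9.5 mSv".

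**The concern.** A protocol should fix one planned enrolment. This one fixes it twice, with different values. A reader cannot tell whether participants 21 to 50 belong to the plan or exceed it.

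Two things depend on the answer. The first is how many people receive a radiation dose given solely for research. The second is the completed enrolment at which the section 8.1 rule is read. The rule is worded as a proportion, so its threshold does not change, but its operating behaviour and the date at which it can be applied do. With two numbers in the text, the rule could also be read at 20 and again at 50. The protocol plans no such double look, but the conflict does not exclude it.

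**Working it through.** **Can either figure be reproduced?** No. The protocol states no significance level, power, effect size or dropout allowance, so neither 20 nor 50 follows from its own inputs. What can be checked is whether the two figures are compatible.

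**Side by side**

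- Difference: 50 − 20 = 30 people. Ratio: 50/20 = 2.5.
- *Modality share or subgroup:* section 2.2 describes its figure as a total, and both places cover both modalities.
- *Recruited versus evaluable:* 20/(1 − d) = 50 gives d = 1 − 20/50 = 0.60. A 60% loss is stated nowhere.
- *Screened versus enrolled:* section 2.2 describes evaluation, consent and enrolment, but gives no second number.
- *Stages:* no cohort, interim look or expansion is described.

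**Radiation** (doses from section 5; the modality mix is not given, so these are the bounds)

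| | 20 people | 50 people |
|---|---|---|
| All PET/MRI, 4.5 mSv each | 20 × 4.5 = 90 person-mSv | 50 × 4.5 = 225 person-mSv |
| All PET/CT, 9.5 mSv each | 20 × 9.5 = 190 person-mSv | 50 × 9.5 = 475 person-mSv |

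The second row is an upper bound only, because PET/CT is reserved for patients with metal implants who cannot have MRI.

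**Timing** (even accrual assumed): 50/4 = 12.5 a year, so 20 is reached after 20/12.5 = 1.6 years and 50 after 4 years.

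**The section 8.1 rule.** The smallest whole number above half is 11 of 20 or 26 of 50. This assumes that every enrolled patient has an evaluable scan and counts as a case. The true identification rates below are assumptions for illustration; the protocol states none. X₂₀ and X₅₀ are binomial, and the 50 include the first 20.

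| Assumed true rate | P(X₂₀ ≥ 11) | P(X₅₀ ≥ 26) | Either, if read at 20 and again at 50 |
|---|---|---|---|
| 0.40 | 0.1275 | 0.0573 | 0.1522 |
| 0.50 | 0.4119 | 0.4439 | 0.5654 |
| 0.60 | 0.7553 | 0.9022 | 0.9311 |

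The last column is P(X₂₀ ≥ 11) plus the sum over k = 0 to 10 of P(X₂₀ = k) × P(at least 26 − k among the next 30). It describes a reading the protocol does not plan.

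**Precision.** At an observed 50%, the exact (Clopper-Pearson) 95% interval is 27.2% to 72.8% with 10 of 20, and 35.5% to 64.5% with 25 of 50.

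**The case against.** The best reply is that this is a small feasibility pilot that disclaims statistical analysis. No hypothesis test or error rate depends on the sample size, and the section 8.1 rule triggers only the planning of a further study. On this view the probabilities are weak evidence of harm: they rest on assumed rates, and at a true rate of 50% a single reading gives almost the same answer (0.41 against 0.44). The double reading is hypothetical, and the all-PET/CT dose is not a realistic plan. The dose per participant is the same under either figure. The word for cases in section 8.1 is itself undefined, so fixing the sample size would not by itself fix the rule's denominator. Finally, some front pages and the content of the schema are not available here and might have carried a linking statement.

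Much of this stands as a limit on the consequences. The probability figures are illustration only, the PET/CT row is a bound, and the undefined denominator is a real further gap. The problem is also an inconsistency between two statements, not a miscalculation. None of it removes the conflict. A pilot needs no power calculation, but it does need one enrolment number, and the two available passages disagree on it. This is not a matter left to a statistical analysis plan either, because the protocol itself states both values.

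**Conclusion.** The concern holds. The protocol states a planned size of 20 and a planned total of 50, both in current text, and no text at hand reconciles them. The size of the discrepancy is 30 people, a factor of 2.5. That part needs no assumptions.

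The case for correcting it rests mainly on the number of people given a research-only radiation exposure, and secondarily on the undetermined enrolment behind the only go criterion. The person-mSv totals depend on an unstated modality mix. The go probabilities depend on assumed true rates, on all scans being evaluable and on all enrolled patients counting as cases. The document does not show which figure is intended, and this review does not choose between them. The correction must be made, since it concerns a basic figure of the trial and costs almost nothing.

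**What to change.** - State one planned enrolment, the one the sponsor intends and the ethics committee approved, in both the synopsis and section 2.2.
- If 20 and 50 are meant as different quantities (for example evaluable and recruited), label each as such in both places and say how they relate.
- Add a clause to section 8.1 saying that the 50% rule is applied once, at that completed enrolment. Keep it as a proportion and do not replace it with a fixed count, because some scans may not be evaluable. The same clause can say who counts as a case.

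The cost is a correction in one of two places, or a label in both, and one added clause. It needs no new data collection or procedures, and the correction itself adds no participants beyond whichever number was approved.

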#### 3. PARTICIPANT SELECTION AND ENROLLMENT PROCEDURES

#### 3.1. Inclusion Criteria

- Patient is ≥ 18 years old at the time of the scan
- Patient with known or suspected cardiac sarcoidosis referred for standard of care F FDG PET/CT

- Patient is capable of complying with study procedures
- Patient can remain still for duration of imaging procedure

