# 6.2. Confidentiality

All data including data forms, PET/MRI reports, and clinical information will be stored in a locked, secure location within the Division of Nuclear Medicine and Molecular Imaging. Data will only be accessed by members of the research team assigned to data collection or analysis. No information derived from this study will be provided to the subject's personal physician, a government agency, or any other person or group.

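### The protocol does not state that FSPG readers are masked to the prior FDG scan or record calls before consensus, so an FDG-independent read is not secured

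*Protocol*

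**What the plan says.** The protocol sets out its reading method in Section 2.2, under Interpretation of Results. Images are "viewed with the software available in the Nuclear Medicine and Molecular Imaging Clinic". Then: "PET images will be interpreted by two radiologists in consensus". A third reader "will serve as referee to achieve consensus".

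The order of work is given ("PET image interpretation will begin with identification of areas of myocardial" FSPG uptake), followed by a global classification of each participant as none, diffuse, focal, or focal on diffuse. The last three "will be considered to be positive findings indicative of cardiac involvement". The call is visual, and no uptake threshold is stated.

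The Methods part of Section 2.2 recruits patients after they have received "FDG PET/CT as standard of care". Section 3.1 admits a "Patient with known or suspected cardiac sarcoidosis referred for standard of care" FDG PET/CT, so some participants may have an established diagnosis.

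The only rule on access to data is in Section 6.2: "Data will only be accessed by members of the research team assigned to data collection or analysis". It concerns confidentiality and places no limit on what an image reader may look at.

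The synopsis gives the primary objective as whether FSPG imaging will identify cardiac sarcoid. Section 8.1 plans a larger study if sarcoid is identified in more than 50% of cases. Section 7 describes a feasibility pilot measured by completed exams and image quality, and Section 8 says no statistical analysis is included.

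**The concern.** When FSPG is read, an FDG result on the same clinical question should already exist for each patient. The FSPG call is a visual judgement, so a reader who knows the FDG result can settle an unclear scan by it. If two readers then agree one joint call and neither has recorded an own call first, no later analysis can separate what FSPG showed from what FDG suggested.

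This bears on the stated objective. Section 2.1 presents FSPG as a tracer that needs no diet or special preparation, unlike FDG. Evidence for using it in that role has to show what it identifies without help from FDG. The four-pattern call is also the only cardiac PET positivity rule in the protocol, and so the likely input to the more-than-50% criterion.

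**Working it through.** **Textual check.** Three questions were put to the protocol.

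1. *Does an FDG result exist before the FSPG read?* Yes, by the recruitment sentence in Section 2.2.
2. *Does any section mask the readers to it?* No. Section 2.2 names the readers, the software, the first step and the positivity rule, and does not mention masking. Section 6.2 limits access to the research team, which does not exclude readers.
3. *Does any section require a recorded call from each reader before consensus?* No. A referee implies that the two readers may differ, but not that their separate calls are kept.

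**Size.** The protocol gives no figure to reproduce: no error rate, no power, no expected positive rate. What follows is an illustration in which every input except the sample sizes and the 50% rule is assumed. The synopsis states 20 patients and Section 2.2 states 50, so both are used.

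- More than 50% means at least 11 of 20 or 26 of 50.
- Assume 20% of scans are equivocal: 0.20 × 20 = 4, and 0.20 × 50 = 10.
- Assume half of these are called positive when masked (2 and 5), and that all follow the FDG result when not masked.
- Shift in the positive count = (equivocal scans that are FDG-positive) − (equivocal scans called positive when masked).

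| n | FDG-positive among equivocal | Shift | Masked counts at which the decision can change |
|---|---|---|---|
| 20 | 0 to 4 of 4 | −2 to +2 (10 points either way) | 9–12 |
| 20 | 1 to 3 of 4 | −1 to +1 (5 points) | 10–11 |
| 50 | 0 to 10 of 10 | −5 to +5 (10 points) | 21–30 |
| 50 | 3 to 7 of 10 | −2 to +2 (4 points) | 24–27 |

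Example for the last column: with n = 20 and a shift of +2, a masked count of 9 or 10 reaches 11. With −2, a masked count of 11 or 12 falls to 10 or below. If half of the equivocal scans are FDG-positive, the net shift is 0.

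The chance that the masked count falls in each window is the binomial sum of C(n,k) p^k (1−p)^(n−k) over the counts k in the window:

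| Assumed masked positive rate p | 9–12 of 20 | 10–11 of 20 | 21–30 of 50 | 24–27 of 50 |
|---|---|---|---|---|
| 30% | 0.11 | 0.04 | 0.05 | 0.01 |
| 50% | 0.62 | 0.34 | 0.84 | 0.42 |
| 70% | 0.22 | 0.10 | 0.08 | 0.01 |

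Falling in a window makes a changed decision possible, not certain: the shift must also be large enough and in the right direction.

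**The case against.** The strongest reply is that this is silence in a feasibility pilot. The protocol plans no analysis and no FDG–FSPG comparison, its stated measure is completed exams of diagnostic quality, and masking could be set in a reading manual. The more-than-50% rule only triggers the planning of another study. It also has no stated reference standard, which masking would not supply.

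Much of this stands. The completed-exam measure is untouched, and a masked positive rate above 50% would still not show that sarcoid was correctly identified. But Section 2.2 does fix who reads, how, and what counts as positive. Consensus reading is a stated choice there, and a later analysis plan cannot recover individual calls that were never recorded.

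Four stronger readings are tempting and are not supported:

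- *The readers will see the FDG scan.* The protocol does not say so, and it does not exclude separate first reads.
- *The positive rate will be inflated.* One can build a case: with a 40% own rate, 50% FDG-positive independently of FSPG, and half of the FSPG-negative, FDG-positive reads switched, the rate becomes 0.40 + 0.60 × 0.50 × 0.50 = 55%. The chance of passing the rule rises from 12.8% to 59.1% with 20 patients. That allows switching in one direction only and assumes that the two tracers are unrelated. The protocol supports neither.
- *Section 8.1 counts the four-pattern call.* That is a plausible inference. The section does not name its input, and Section 2.2 also grades T2 and late-enhancement MRI findings and extra-cardiac disease.
- *The PET call must be locked before MRI grading, or all clinical data withheld.* These are design preferences. Independence from FDG does not require them.

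**Conclusion.** The point holds as a gap in protection: the stated reading procedure does not secure an FSPG call that is independent of FDG, and the loss could not be repaired after the reads. It is not a demonstration of bias, and neither its direction nor its size follows from the protocol.

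Under the assumed 20% equivocal share and complete following of FDG, the shift is at most 10 percentage points either way and can be zero. It bears on the more-than-50% decision mainly when the masked positive rate is near 50%. That further assumes that the pattern call is what the rule counts. The change should be made because it is cheap before reading starts and impossible to make good afterwards.

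**What to change.** In Section 2.2, Interpretation of Results, replace the consensus sentence with a rule to this effect:

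- Each of the two named readers, masked to the FDG PET/CT images and report, independently records and locks the four-pattern call.
- The third reader, masked in the same way, adjudicates disagreements only.
- The adjudicated masked call is the one counted for the more-than-50% criterion in Section 8.1.

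The MRI or CT from the FSPG examination, anatomic and cardiac, may stay available to the readers.

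The cost is somewhat more reading time and the work of de-identifying the studies. The protocol does not say who reports the clinical FDG scan. If a named reader does, de-identified studies or a delay before the FSPG read will be needed. Patients, scans and sample size are unaffected. The change does not provide a reference standard, which is a separate matter.

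### Any myocardial FSPG uptake is read as positive; this fits a target of sarcoid or inflammation, but not a sarcoid-specific goal, primary objective or go criterion

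*Protocol*

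**What the plan says.** **The read.** Under Interpretation of Results in Section 2.2, myocardial uptake is sorted into "one of four patterns (none, diffuse, focal, or focal on diffuse) for each participant". The three patterns other than none are pooled: "uptake will be considered to be positive findings indicative of cardiac involvement". The call depends only on whether uptake is seen. Its cause does not enter.

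**The target.** The Protocol describes it in two ways.
- The broad form is in the title and in Section 1, which expects that increased "uptake will be detected in cardiac sarcoid or inflammation using PET/MRI or PET/CT".
- The narrow form is in the synopsis table and Section 8.1. The synopsis goal is to let referring physicians "provide their patients a specific molecular imaging test for sarcoidosis", and its primary objective is to identify cardiac sarcoid. Section 8.1 makes a larger study depend on sarcoid being found in over half of the participants.

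**The background.** Section 2.1 states: "Myocardial inflammation can also result from other causes including myocarditis". It also says that FSPG "has also demonstrated increased uptake in inflammation and infection".

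**The MRI read.** Section 2.2 adds: "The pattern of LGE will be classified as either CAD type or non-CAD type as described previously". Nothing in the Protocol connects that label to the PET call.

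**The concern.** The read answers whether there is myocardial FSPG uptake. The goal, the primary objective and the go criterion ask whether there is sarcoid. By the Protocol's own background these are different questions, and no step leads from one to the other.

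The decision to run a larger study is at stake. If the numerator in Section 8.1 is any positive uptake, the error runs the wrong way: each participant with non-sarcoid or background uptake helps to pass the criterion and weakens the evidence about sarcoid. The pilot could pass and be reported as progress toward a sarcoid-specific test on data that cannot show it.

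**Working it through.** The Protocol gives no rate, power or error level, and Section 8 says that no statistical analysis is included. There is therefore no figure to reproduce. The check is a comparison of the text, followed by an illustration on stated assumptions.

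**1. Does the read match each statement of the target?**

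| Place | What it asks for | Met by any-uptake read? |
|---|---|---|
| Section 1, hypothesis | uptake in sarcoid or inflammation | yes |
| Section 7, purpose | completed exams, diagnostic images | not affected |
| Synopsis, primary objective | identification of cardiac sarcoid | no |
| Synopsis, goal | test specific for sarcoidosis | no |
| Section 8.1, go criterion | sarcoid found in over 50% | no sarcoid call is defined |

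**2. What would counting any uptake do to the go criterion?** Section 8.1 does not say that positive uptake is its numerator, but the Protocol defines no other PET call. Take that reading and let

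- prev = share of participants with cardiac sarcoid (assumed 25%, 40% or 50%)
- Se = share of them with uptake (assumed 0.90)
- f = share of the others with any uptake (assumed 0 to 0.6)

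Then P(pos) = prev × Se + (1 − prev) × f, and PPV = prev × Se / P(pos). P(go) is the binomial chance of at least 11 positives among 20 (the synopsis sample size) or at least 26 among 50 (the number in Section 2.2).

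Worked case with prev 0.40 and f 0.4: P(pos) = 0.40 × 0.90 + 0.60 × 0.4 = 0.36 + 0.24 = 0.60, and PPV = 0.36 / 0.60 = 0.60.

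| prev | f | P(pos) | PPV | P(go), n=20 | P(go), n=50 |
|---|---|---|---|---|---|
| 0.25 | 0 | 0.225 | 1.00 | 0.002 | 0.000 |
| 0.25 | 0.2 | 0.375 | 0.60 | 0.085 | 0.026 |
| 0.25 | 0.4 | 0.525 | 0.43 | 0.502 | 0.585 |
| 0.25 | 0.6 | 0.675 | 0.33 | 0.921 | 0.992 |
| 0.40 | 0 | 0.360 | 1.00 | 0.065 | 0.015 |
| 0.40 | 0.2 | 0.480 | 0.75 | 0.343 | 0.335 |
| 0.40 | 0.4 | 0.600 | 0.60 | 0.755 | 0.902 |
| 0.40 | 0.6 | 0.720 | 0.50 | 0.970 | 0.999 |
| 0.50 | 0 | 0.450 | 1.00 | 0.249 | 0.197 |
| 0.50 | 0.2 | 0.550 | 0.82 | 0.591 | 0.716 |
| 0.50 | 0.4 | 0.650 | 0.69 | 0.878 | 0.979 |
| 0.50 | 0.6 | 0.750 | 0.60 | 0.986 | 1.000 |

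At each prevalence, PPV falls and P(go) rises as f rises. Enrolling 50 rather than 20 does not protect: once P(pos) is above one half, the larger sample passes more surely.

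**3. Diffuse-only patients at the boundary.** With 11 of 20 positive (55%), recoding one diffuse-only patient as not positive gives 10/20 = 50%, which no longer exceeds 50%. With 26 of 50 (52%) it gives 25/50 = 50%. The denominator must stay fixed: dropping the patient altogether gives 10/19 = 52.6% or 25/49 = 51.0%, and both still pass. This shows how close the boundary is, not how often such a patient occurs.

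**The case against.** The best defence is that the read does what the study set out to do. The title, the hypothesis and the Methods in Section 2.2 all include inflammation, the call is worded as cardiac involvement rather than sarcoid, and Section 7 describes a feasibility pilot. The goal may be a programme aim, with specific meaning no more than dedicated. Section 8.1 never equates finding sarcoid with any uptake, an unseen analysis plan may add tabulations, and the rates above are assumed.

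Much of this stands. The reading rule is not an error in itself, and the rates only illustrate direction. But a loose reading of the goal does not rescue Section 8.1, which needs a sarcoid call that the Protocol does not define. The primary objective also names sarcoid without qualification. These statements are fixed in the Protocol.

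A reader might go further and infer that the MRI read already marks segments as ischaemic, so that uptake confined to them should be struck from the positives. The document does not support this:
- Section 2.2 grades the presence of late enhancement by segment but does not say that CAD or non-CAD type is assigned by segment.
- Late enhancement exists only for PET/MRI participants given contrast. Section 4 makes contrast optional, and patients with implants have PET/CT. Excluding on it would put two definitions of positive into one fraction.
- It would not separate sarcoid from myocarditis, the one alternative cause that the Protocol names.
- Nothing says that FSPG accumulates in ischaemic scar.

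A reader might also want a fixed uptake threshold, such as LV blood pool, to separate none from diffuse. The document gives no basis for one. Nor is a diffuse-only patient without a positive segment a contradiction, because the global pattern and the focal segment map are separate outputs.

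**Conclusion.** The point holds as a mismatch between the read and the narrower statements of purpose. The any-uptake call is adequate for sarcoid or inflammation. It cannot support the synopsis goal, the primary objective or Section 8.1 as these are worded.

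That the go criterion becomes easier to pass as non-sarcoid uptake increases rests on one reading, namely that Section 8.1 counts positive uptake. The size rests on assumed rates. At 0.90 sensitivity and 25% prevalence, for example, non-sarcoid positivity of 0.6 gives a PPV of 0.33 with a chance of passing of 0.92 (20 patients) or 0.99 (50 patients). The direction does not depend on the particular values.

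The point is moderate: it limits what the pilot can conclude, not how it is conducted.

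**What to change.** 1. Restate the synopsis goal, the primary objective and the Section 8.1 criterion as detection of myocardial FSPG uptake consistent with active inflammation, in people with known or suspected cardiac sarcoid.
2. Report the four uptake patterns separately. Give the Section 8.1 fraction twice, with diffuse-only patients counted as positive and as not positive, over the same denominator.
3. For participants who had contrast MRI, tabulate the PET result against LGE pattern (CAD or non-CAD type) at patient level. Label the table descriptive and leave the positivity call unchanged.

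The first change is wording only, and the second uses the four-pattern read already planned. The third needs one LGE pattern per participant with contrast MRI and will be incomplete for the rest. No extra scans or patients are needed. The price is a less ambitious goal and a possibly lower positive fraction in one of the two displays.
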